7.4. Study Discontinuation

The 50 mg QD dose is well tolerated. Some patients are being treated for more than 2 years at that dose. No DLT has been reported. The study protocol plans some early discontinuation criteria and specifically in case of modification of LFTs in accordance to the pre-clinical findings.

In addition, all safety data will be thoroughly reviewed by the DSMB. Part of the DSMB duties is to review occurrence of adverse events which character, severity or frequency is new in comparison to the existing risk profile. In such case, recommendations from the DSMB may lead to either additional stopping rules up to study discontinuation.

7.5. End of Trial

In the frame of the ABX464-401 study, the end of trial will occur once the last randomized patient has performed at least the safety follow-up visit of 21 days after the last study drug intake, and depending on their status during the study, the 4 months follow-up visit/call.

Then all data will be analyzed and embed in a clinical study report.

8. ADVERSE EVENTS (AE) AND SERIOUS ADVERSE EVENTS (SAE)

The investigator is responsible for the detection and documentation of events meeting the criteria and definition of an AE or SAE. During the study, in case of a safety evaluation, the investigator or site staff will be responsible for reporting AEs and SAEs, as detailed in this section of the protocol.

All adverse events (Serious and non-serious) will be collected from the time of signing of ICF and until D48 visit.

Any disease progression will be both reported in the eCRF as an adverse event and documented in the efficacy section.

8.1. Definitions

8.1.1. Definition of an Adverse Event (AE)

Any untoward medical occurrence in a patient or clinical investigation patient administered a pharmaceutical product and which does not necessarily have to have a causal relationship with this treatment.

An AE can therefore be any unfavorable and unintended sign (including an abnormal laboratory finding), symptom, or disease (new or exacerbated) temporally associated with the use of a medicinal product, whether or not considered related to the medicinal product.

Note: The official definition also extends to AEs occurring in the placebo arm. Because of regulatory requirements, events occurring during pre-and post-treatment periods will also be designated as AEs. Therefore, reporting of such events, AEs and SAEs, will start when the patient is enrolled into the study (date of signature of the informed consent) up until 4 Weeks after the end of the treatment visits. The period after discontinuing study drug may be extended if there is a strong suspicion that the drug has not yet been eliminated.

8.1.2. Definition of an Adverse Drug Reactions (ADR)

A response to a medicinal product which is noxious and unintended.

Suggesting that there is at least a reasonable possibility or suspicion of a causal relationship between the medicinal product and an adverse event.

8.1.3. Definition of a Serious Adverse Event (SAE) or Serious Adverse Drug Reaction (SADR)

A serious adverse event (experience) or reaction is any untoward medical occurrence that, at any dose:

a) Results in death

NOTE: Death is an outcome of an AE, and not an AE in itself. Event which led to death should be recorded with fatal outcome.

b) Is life-threatening

NOTE: The term 'life-threatening' in the definition of 'serious' refers to an event in which the patient was at risk of death at the time of the event. It does not refer to an event, which hypothetically might have caused death, if it were more severe.

c) Requires hospitalization or prolongation of existing hospitalization

NOTE: In general, hospitalization means that the patient has been detained (usually involving at least an overnight stay) at the hospital or emergency ward for observation and/or treatment that would not have been appropriate in the physician's office or out-patient setting. Complications that occur during hospitalization are AEs. If a complication prolongs hospitalization or fulfills any other serious criteria, the event is serious. When in doubt as to whether "hospitalization" occurred, or was necessary, the AE should be considered serious.

Hospitalization for Covid-19 infection consequences will be reported as a Serious Adverse Event.

Hospitalization for elective treatment of a pre-existing condition that did not worsen after informed consent was given is not considered serious.

d) Results in persistent or significant disability/incapacity,

NOTE: The term disability means a substantial disruption of a person's ability to conduct normal life functions. This definition is not intended to include experiences of relatively minor medical significance such as uncomplicated

headache, nausea, vomiting, diarrhea, influenza, and accidental trauma (e.g. sprained ankle) which may interfere or prevent everyday life functions but do not constitute a substantial disruption.

- e) Is a congenital anomaly/birth defect
- f) Is another medically important condition: This refers to an AE that may not be immediately life-threatening or results in death or hospitalization but may jeopardize the patient or may require intervention to prevent one of the outcomes listed above. Based on medical and scientific judgment this should usually be considered serious.

If there is any doubt about whether or not an AE is serious, the investigator should contact the sponsor.

8.1.4. Definition of a Suspected Unexpected Serious Adverse Reaction (SUSAR)

A Suspected Unexpected Serious Adverse Reaction (SUSAR), is a serious adverse reaction (SAR) for which a reasonable causal relationship with the medicine use is suspected but not confirmed. Unexpected in this context means not consistent with the applicable product information (e.g. investigator's brochure for an unapproved investigational product or summary of product characteristics (SmPC) for an authorised product).

8.2. Events and/or Outcomes Not Qualifying as SAEs

Any hospitalization, or prolongation of hospitalization due to the circumstances listed below, will not be reported as SAE:

- planned medical/surgical procedure;
- planned medical/surgical admission (planned prior to entry into study, appropriate documentation required), for the disease under study;
- Administrative or social reasons (e.g. lack of housing, economic inadequacy, care-giver respite, family circumstances).

8.3. Events or Outcomes Qualifying as AEs or SAEs

8.3.1. COVID-19 related AE/SAEs

All COVID-19 related AE/SAEs will be recorded.

8.3.2. Clinical laboratory parameters

Abnormal laboratory findings (e.g., clinical chemistry, hematology) or other abnormal assessments (e.g. vital signs) that are judged by the investigator as **clinically significant** will be recorded as AEs or SAEs if they meet the definitions of section 8.1. Clinically significant abnormal laboratory findings or other abnormal assessments that are detected during the study or are present at informed consent and significantly worsen during the study will be reported as AEs or SAEs. Clinically significant abnormal laboratory findings or other abnormal assessments that are associated with the disease being studied and are present at the start of the study will be recorded as medical history and will be reported as AEs or SAEs in case of worsening.

8.3.3. Pregnancy report

Patients who become pregnant at any time will be immediately withdrawn from participation in the study. All appropriate withdrawal assessments may be performed at the discretion of the investigator.

The investigator will collect pregnancy information on any woman patient or partner of a male patient, who becomes pregnant and their partner while participating in this study. The investigator will record pregnancy information on a specific pregnancy notification form and submit it to ABIVAX or its designee within 24 hours after knowledge of a patient's or partner's pregnancy. The patient or partner will also be followed to determine the outcome of the pregnancy, be it full-term or prematurely terminated. Information on the status of the mother and child will be forwarded to ABIVAX or its designee. Follow-up will end 6 to 8 weeks following the estimated delivery date.

While pregnancy itself is not considered to be an AE or SAE, any pregnancy complication or elective termination of a pregnancy for medical reasons will be recorded as an SAE. A spontaneous abortion is always considered to be an SAE and will be reported as such.

The time period for collecting pregnancy information is identical to the time period for collecting AEs, as stated in Section 8.4, Time Period, Frequency, and Method of Detecting AEs and SAEs.

8.4. Adverse events from previous clinical trials

More than 300 patients have already received ABX464 at different dose levels and for different durations. ABX464 is generally well-tolerated. The most frequently reported side effects with ABX464 treatment are:

- Occuring in more than 10% of the patients: headache, nausea, vomiting, gastrointestinal tract disorders (upper abdominal pain).

All these adverse reactions were either mild or moderate and only 2 led to treatment stop. The frequency of these adverse events seemed to be dose-related, starting from 75mg and higher.

- Occuring in less than 10% of the patients: Diarrhea, Fatigue, Edema, Muscle and joint pain, Dizziness, Fever, Skin rash, Pruritus, Conjunctivitis.

8.5. Time Period, and Frequency of Detecting AEs and SAEs

All AEs and SAEs occurring from the time a patient consents to participate in the study until 21 days after he or she has completed or discontinued the investigational product must be recorded in the Patient's eCRF.

Moreover, any occurrence of pregnancy within 6 months post stopping dosing must be reported.

Importantly, SAEs will have to be reported, **either by email or by Fax, to IntuVigilance Limited within 24 hours of awareness of an SAE.**

IntuVigilance Limited

UK:

[name]
[name]
[name]

Hotline [contact]

Email Address: [contact]

[contact]

Legislative guidance requires the investigator to also ensure that any **related** SAEs are reported after the patient finished the study if the investigator becomes aware of them.

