To evaluate the time to application of *invasive and non-invasive mechanical ventilation (IMV and NIV, respectively) or high flow oxygen therapy* (excluding simple oxygen supplementation) and oxygen supplementation during the study compared to {Standard of care + placebo} treated group.

- *Time to assisted ventilation and oxygen supplementation (log rank) from baseline.*

To assess the IMV and/or NIV duration compared to {Standard of care + placebo} treated group.

- *Number of days of assisted ventilation.*

To assess the oxygen supplementation (>3L/min) duration compared to {Standard of care + placebo} treated group.

- *Number of days of oxygen supplementation.*

To assess the hospital stay duration in both treatment groups for patients hospitalized because of Covid-19 infection consequences compared to {Standard of care + placebo} treated group.

- *Number of days at the hospital from admission to discharge.*

To evaluate the effect of ABX464 on miR-124 expression in whole blood (PAXgene®) vs placebo (in selected sites and in hospitalized patients).

- *Change from baseline in microRNA-124 levels in total blood (PAXgene®) at D0, D7 and D28.*

To assess the change over time in CRP, Troponin I & T and D-dimer levels compared to {Standard of care + placebo} group.

- *AUC and % of change from enrolment in CRP, Troponin I & T and D-dimer levels.*

To evaluate the prevention of Covid-19 related deaths compared to {Standard of care + placebo} group

- *Time to death and mortality rate (all causes, and Covid-19 related).*

To evaluate the improvement in the 7-point ordinal scale during the course of the study compared to {Standard of care + placebo} group.

- *Time to improvement of one level in è-point ordinal scale.*

To evaluate SARS-CoV-2 infection in subjects during the course of the study compared to {Standard of care + placebo} group.

- *SARS-CoV-2 virus in nasopharyngeal sample and/or in blood at Day 0, 7 (hospitalized patients), 14, 21, and 28.*

To evaluate outpatients SpO₂ evolution from D0 to D14

- *Change in SpO₂ values from D0 to D14 in the outpatient's population.*

To evaluate the long-term effect of ABX464 on all cause mortality from first study drug intake to 3-months follow-up visit

- *Rate of participants deceased during the course of the study and follow-up, and time to event (in weeks).*

To evaluate the safety of ABX464 in study patients (from D0 to D48)

- *Number and rates of participants with Treatment Emergent Adverse Event*

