7. STUDY COMPLETION

7.1. Patient Completion

Treatment with ABX464/Placebo shall continue until D28, except if a patient fulfils a premature discontinuation criterion (defined below).

Patients should be instructed to take their last study drug dose until the day before D28 visit. Should a patient start to take the treatment at D1, s/he will be instructed to take the last dose on D28.

After D28, patients will come back 21 days after the last study drug intake to perform an onsite safety follow-up visit at D48.

Following this visit, long-term follow-up for respiratory function exploration will be performed on-site for patients having been hospitalized during the study. This follow-up will take place 3 months after the last study drug intake.

For outpatients, a remote telephone follow-up will be performed 3 months after the last study drug intake.

Then, patients will exit the study and will be treated/follow-up according to the site standard of care.

Given the fact that the pulmonary function follow-up is exploratory and depends on the patient status during the study, a patient status is COMPLETE when the treatment period of 28 days is fulfilled, and the safety follow-up of 21 days is performed.

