For visit windows multiple records may exist in one particular visit window for a particular assessment (i.e. laboratory assessments). The assessment closest to the actual target visit day is chosen as the analyzable record for both continuous variables and categorical variables. If two assessments have the same distance, then the earlier one by relative study day will be chosen as the analyzable record.

Early discontinuation visit remapping

Patients who prematurely discontinue from the study for any reason, will be scheduled for a Safety follow-up visit approximately 21 days following their last study drug intake, at which time all of the assessments listed for that visit will be performed. This visit will be assigned to Visit 6 (EoS).

Table 2 Visit Windows

Study Period	Visit Name	Target Visit Day	Start Day of Visit Window	End Day of Visit Window
Treatment	Visit 1	Day 1	1	1

Study Period	Visit Name	Target Visit Day	Start Day of Visit Window	End Day of Visit Window
	Baseline	Defined as the last available assessment (scheduled or unscheduled) on Day 1		
	Visit 2	Day 7	2	10
	Visit 3	Day 14	11	18
	Visit 4	Day 21	19	25
	Visit 5 (EoT)	Day 28	26	Date of study drug return.
	End of Treatment	End of Treatment is defined as the last available assessment (scheduled or unscheduled) assigned to Treatment Period.		
Safety Follow-up	Visit 6	Day 48	Date of study drug return + 1 day	Target visit day + 30 days
	Visit 7 (Long-term FUP)	Date of study drug return + 90 day	Target visit day - 10 days	Target visit day + 30 days
	End of Study	End of Study is defined as the last available assessment (scheduled or unscheduled) assigned to the Overall Study Period.		

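### Protocol Sections 8, 8.1.1 and 8.5 give conflicting ends for AE/SAE collection and leave the rule for early stoppers unclear; separately, the SAP's crude AE percentages have no stated cut-off or allowance for shorter observation

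*Protocol*

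**What the plan says.** Protocol Section 8 opens with one end of collection: "All adverse events (Serious and non-serious) will be collected from the time of signing of ICF and until D48 visit". The note in Section 8.1.1 gives another, with AE and SAE reporting running "up until 4 Weeks after the end of the treatment visits". Section 8.5 gives a third, for AEs and SAEs alike: "until 21 days after he or she has completed or discontinued the investigational product must be recorded". No section says which governs. The safety objective in Section 2.2 covers D0 to D48.

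For completers, Section 7.1 sets both the last dose ("Patients should be instructed to take their last study drug dose until the day before D28 visit") and the safety visit ("patients will come back 21 days after the last study drug intake to perform an onsite safety follow-up visit at D48"). Section 7.2 asks every patient, including those who stop prematurely, to attend a safety visit 21 days after the last dose. SAP Section 4.2.3 says that patients who leave the study early "will be scheduled for a Safety follow-up visit approximately 21 days following their last study drug intake", and it assigns that visit to Visit 6.

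SAP Section 4.11.1 defines a TEAE by its start only: onset or worsening after at least one dose. It gives no last day. The AE summaries are numbers and percentages of patients by group, plus event counts, produced separately up to Day 28 and after Day 28. Section 4.11 bases them on the whole Safety Set. Neither section states a person-time denominator or limits a table to patients still observed.

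**The concern.** There are two separate problems.

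The first is the contradiction. A completer's event on D52 would be recorded at a site that follows Section 8.1.1 and not at a site that follows Section 8 or 8.5. Nothing in the TEAE definition would then keep that event out of the tables. For a patient who stops drug early, a site cannot tell whether to keep recording to Day 48 or to stop 21 days after the last dose.

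The second does not depend on how many rules there are. A collection end tied to the last dose gives early stoppers a shorter observation time than completers, yet the crude percentages count both as if fully observed. The after-Day-28 table is the most exposed.

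Safety is the only objective that SAP version 5.0 keeps (Sections 2.1 to 2.3), so these tables carry what remains of the comparison between arms.

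**Working it through.** **Inputs.** The three collection ends (Protocol 8, 8.1.1, 8.5); last dose and visit days (7.1); the early stopper's safety visit (7.2, SAP 4.2.3); the D0 to D48 objective (2.2); crude percentages split at Day 28 (SAP 4.11.1). The documents give no discontinuation rates, so step 5 rests on assumptions.

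**1. The plan's own figure.** A completer's last dose is the day before the D28 visit: D27 + 21 = D48, as Section 7.1 states. A patient who starts on D1 takes the last dose on D28: D28 + 21 = D49, inside the ±2 day window. Sections 8 and 8.5 therefore agree for completers.

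**2. Section 8.1.1.** D28 + 28 = D56, or D54 to D58 with the ±2 day window on the D28 visit. That is 56 − 48 = 8 days beyond the other two rules.

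**3. Early stopper under the 21-day rule.** For a last dose on day x, collection ends on day x + 21. Observation after Day 28 is max(0, x + 21 − 28), out of 48 − 28 = 20 days.

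| Last dose | Collection ends | Share of 48 days | Shortfall against D48 | Days observed after D28 |
|---|---|---|---|---|
| D3 | D24 | 50% | 24 | 0 |
| D7 | D28 | 58% | 20 | 0 |
| D10 | D31 | 65% | 17 | 3 |
| D14 | D35 | 73% | 13 | 7 |
| D21 | D42 | 88% | 6 | 14 |
| D27 | D48 | 100% | 0 | 20 |

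For the D10 case, Section 8 gives D48 if its D48 visit means the calendar day. Section 8.1.1 gives D56 if the D28 visit is kept, or D10 + 28 = D38 if the end-of-treatment visit is held when drug stops.

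**4. Which table is affected.** A patient who stops on or before D7 and is followed only under the 21-day rule has no observation after Day 28. The SAP counts Visit 1 as Day 1 (Section 4.2.1), which moves this threshold by a day, hence about D7. Any stop on or after D7 still covers the whole period up to Day 28, so the loss then falls on the after-Day-28 and whole-study tables.

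**5. Effect on the arm comparison (illustration).** Assume the same true 48-day AE risk F in both arms, a constant hazard h = −ln(1 − F)/48, and a fraction d stopping on day x and followed for x + 21 days. The crude rate is (1 − d)·F + d·[1 − exp(−h(x + 21))].

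- F = 30%, x = 7: h = 0.00743 per day, and the risk over 28 days is 18.8%.
- 10% stopping in both arms: 0.9 × 30% + 0.1 × 18.8% = 28.9% in each, with mean follow-up 46.0 days in each. The artificial difference is zero.
- 20% against 10% stopping: 0.8 × 30% + 0.2 × 18.8% = 27.8% against 28.9%, a difference of 1.1 points, with mean follow-up 44.0 against 46.0 days.
- Over stop days D3 to D14, F from 30% to 60%, and 15% or 20% against 10% stopping, the artificial difference runs from 0.4 to 2.3 points.
- After-Day-28 table alone, with an assumed 10% risk over those 20 days and stops on D7: 0.8 × 10% = 8.0% against 0.9 × 10% = 9.0%, a difference of 1.0 point.

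**The case against.** The strongest reply is that Sections 8 and 8.5 need not conflict at all. Section 8 refers to the D48 visit rather than to calendar Day 48, and SAP 4.2.3 assigns the 21-day visit of a patient who leaves the study to Visit 6. On that reading the two agree for early discontinuers as well as completers, and only the note in Section 8.1.1 is out of line. This largely stands. It is why early stopping is called unclear here rather than contradictory in every case. But it is an inference that no section states, and it sits awkwardly with an objective worded as D0 to D48.

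Stopping drug is also not the same as leaving the study. SAP 4.2.3 covers only patients who leave, and the flow chart (Section 5.1) schedules AE recording through D48 without cancelling visits for those who only stop drug. Such a patient may be fully observed. That stands too: the loss in step 3 applies only to patients followed solely under the 21-day rule.

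There are partial safeguards. Related SAEs must still be reported later if the investigator learns of them (Section 8.5), and the 3-month contact goes ahead unless consent is withdrawn (Section 7.2). SAP 4.3.1 uses the end-of-study date when classifying events with partial dates. That limits the loss for related SAEs and deaths. It does not give AEs in general a common cut-off.

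Finally, a fixed lag after the last dose is a coherent safety window. That is so, provided the tables allow for the unequal observation it creates.

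**Conclusion.** The contradiction is established. Three statements of the collection end stand in the protocol, Section 8.1.1 departs from the other two by about 8 days for completers, and the rule for early stoppers is not stated clearly. The SAP does not settle it, because its TEAE definition has no last day.

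The denominator problem is real but conditional. It needs patients who stop early and are followed only under the 21-day rule; such a patient stopping by about D7 adds to the after-Day-28 denominator and cannot add to its numerator.

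Three stronger conclusions are tempting, and the documents do not support them:

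- A reader might infer that the conflicting dates cause the unequal follow-up. They do not. The 21-day rule would do so alone, and a calendar D48 rule for everyone would not.
- A reader might infer that AE rates on ABX464 are biased low. That needs stopping to differ by arm in frequency or timing. No rates are given, and Section 8.4 reports that only 2 of the most frequent earlier reactions led to stopping treatment. Under the assumed imbalances the effect is modest, about 0.4 to 2.3 points, and it is zero when stopping is equal in frequency and timing.
- A reader might infer from the metabolite's half-life that 21 days is too short. The five-half-lives text in exclusion criterion 10 concerns other products taken before baseline, not AE follow-up.

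**What to change.** **Protocol.** Reconcile Sections 8, 8.1.1 and 8.5 into one end of AE/SAE collection. State expressly how it applies to patients who stop drug but stay in the study and to those who leave the study.

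**SAP.** Apply the same cut-off to the TEAE definition and tables in Section 4.11.1. Report observation time by arm. For the after-Day-28 table, either give exposure-adjusted rates or limit the denominator to patients still under observation.

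**Optional.** Ask about AEs up to D48 at the 3-month contact that is already planned. The downside is less precise retrospective recall.

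**Cost.** A wording amendment and a few extra table columns. The study was terminated after the DSMB meeting of 4 March 2021, so collection may already be over. In that case the SAP changes are the part that can still be made, and the report should state which collection end the sites followed. A common cut-off in the analysis cannot recover events that were never recorded.
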